### Hypothesis Testing

The null and alternative hypotheses for testing non-inferiority of the Test lens relative to the Control lens with respect to logMAR visual acuity are as follows:

$$H_0: \mu_T - \mu_C \geq 0.05$$
$$H_A: \mu_T - \mu_C < 0.05$$

Where,  $\mu_T$  represents the mean logMAR VA score for the Test lens and  $\mu_C$  represents the mean logMAR VA score for the Control lens. Non-inferiority will be declared if the upper bound of the 2-sided 95% confidence interval of the difference (Test – Control) is less than 0.05. If non-inferiority of the Test lens over Control lens is met, then superiority will be assessed. If the upper bound is less than 0, then superiority of the Test lens over the Control lens will be established.

### Primary Safety Analyses:

Primary safety analysis will be conducted on the safety population based on treatments actually received by subjects.

### Lens Fit Acceptance

Lens fit acceptance will be analyzed using a Bayesian beta-binomial model with correlated binary data.

### The Model:

Let  $Y_1$  and  $Y_2$  denote the binary outcomes of lens fit acceptance (Yes/No) in left and right eyes, respectively, across dispensing and follow-up visits when wearing a study lens. Considering the correlation,  $\rho$ , between  $Y_1$  and  $Y_2$ , the distribution of the sum  $Y = Y_1 + Y_2$  is obtained by the mixture of two variables. One of them follow a binomial distribution  $Bin(2, p)$  with mixing probability  $(1 - \rho)$  and the other one follows a modified Bernoulli distribution,  $MBern(p)$ , taking value 0 and 2 rather than conventional 0 and 1, with mixing probability  $\rho$ :

$$P(Y = y | p, \rho) = (1 - \rho)Bin(2, p)I_{A1} + \rho MBern(p)I_{A2},$$

where  $I_{A1} = \{0, 1, 2\}$ ,  $I_{A2} = \{0, 2\}$  and  $p$  is the probability of success (i.e., acceptable lens fitting).

## Clinical Study Protocol Johnson & Johnson Vision Care, Inc.

To overcome the complexity of the mixture likelihood a latent variable  $Z_i$ ,  $i = 1, 2$  is introduced in the model to indicate in which component of the model the observation  $y_i$ ,  $i=1, 2$ , belongs to, that is,

$$Z_i = \begin{cases} 1, & \text{if the observation belong to the MBern}(p), \\ 0, & \text{if the observation belong to the Bin}(2, p) \end{cases}$$

The joint distribution of the augmented data  $(Y_i, Z_i)$ ,  $i = 1, 2$ , is given by

$$\begin{aligned} P(Y = y_i, Z = z_i | p, \rho) \\ = \rho^{z_i} p^{y_i z_i / 2} (1 - p)^{(2 - y_i) z_i / 2} (1 - \rho)^{1 - z_i} \binom{2}{y_i} p^{y_i(1 - z_i)} (1 - p)^{(2 - y_i)(1 - z_i)} \end{aligned}$$

The probability  $p$  links to the regression variables through a logit transformation as follow:

$$\text{logit}(p) = \beta_0 + \beta_1 \text{lens}$$

It is assumed that  $\beta_0$ ,  $\beta_1$  and  $\rho$  to be independent with a non-informative prior  $N(0, 1000)$  for  $\beta_0$  and  $\beta_1$ , and  $\text{beta}(0.5, 0.5)$  for  $\rho$ . The Metropolis sampler algorithm as implemented in the SAS/STAT MCMC Procedure will be used to estimate the posterior distributions of the parameters  $(\beta_0, \beta_1, \rho)$ . Inferences will be made based on a posterior credible interval for the relevant parameters.

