### Lens Fit Acceptance

Unacceptable lens fitting is a binary response as  $Y = 1$  if a subject eye has an unacceptable fitting and  $Y = 0$  otherwise. From the historical data there was no unacceptable lens fitting for both study lenses. Assuming no difference between study lenses and a correlation of 0.70 between left and right eyes within the same subject, a total of 2000 replicating trials were simulated with an unacceptable fitting rate of 5% (worse-case scenario). Given the rare event binary outcome of fit acceptance, each replicated sample was analyzed using a Bayesian beta-binomial model with correlated binary data. Sample size was estimated to achieve a minimal statistical power of 80% with a non-inferiority margin of 10% (Test – Control) based on the simulated data. For each simulated trial, the lower bound of the 95% central posterior credible interval constructed for the percentage difference was compared to the 10% margin. With the proposed sample size, there was at least 80% of the estimated 95% credible intervals with upper bound being below 10%.

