### Bayesian Estimation and Statistical Evaluation of Hypothesis:

Non-inferiority of the Test lens relative to the Control lens with respect to lens fit acceptance will be evaluated using Bayesian statistics. The null and alternative hypotheses for evaluating non-inferiority of the Test lens relative to the Control lens with respect to lens fit acceptance are as follows:

$$\begin{aligned} H_0: p_T - p_C \geq 0.1 \\ H_A: p_T - p_C < 0.1, \end{aligned}$$

where  $p_T$  and  $p_C$  are the probability of event (i.e., unacceptable lens fitting) for Test lens and Control lens, respectively. Based on Bayesian posterior probability distribution of the proportion difference  $(p_T - p_C)$ , non-inferiority is interpreted as 95% probability of Test being no worse than Control by 10% (i.e.,  $p_T - p_C < 0.1$ ) with respect to unacceptable lens fitting rate. If the upper bound of the 95% central posterior credible interval is below 0.1, it can be concluded that there is 95% probability that the Test lens is non-inferior to the Control lens based on the observed sample.

In the case of all eyes have an acceptable lens fit (i.e., zero unacceptable lens fit), a Bayesian hierarchical model accounting for zero event problem will be considered. Details of this model will be provided in the stand-alone SAP.

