### Biomicroscopy (Slit Lamp Findings)

Biomicroscopy will be analyzed using the same Bayesian beta-binomial model as described for lens fit acceptance. The proportion of eyes with clinically significant slit lamp findings (i.e., Grade 3 or higher, or significant corneal infiltrates) across study visits will be modeled.

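### The printed density for the two-eye safety model omits a support restriction: a one-eye event gets weight it should not have, and literal coding would cost some power

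*Combined protocol and SAP*

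**What the plan says.** Section 14.5, The Model (lens fit acceptance), takes Y as the sum of the two eyes' binary outcomes. Y follows Bin(2, p) with probability 1 − ρ, and with probability ρ a modified Bernoulli, MBern(p), "taking value 0 and 2 rather than conventional 0 and 1". The mixture formula carries support indicators {0, 1, 2} and {0, 2}.

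The plan then adds a latent Z (1 for MBern, 0 for the binomial). After the words "The joint distribution of the augmented data" it prints

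`ρ^z · p^(yz/2) · (1−p)^((2−y)z/2) · (1−ρ)^(1−z) · C(2,y) · p^(y(1−z)) · (1−p)^((2−y)(1−z))`

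with no support indicator. The coefficients and ρ are taken "to be independent with a non-informative prior" (normal for the coefficients, beta(0.5, 0.5) for ρ), and the posterior is sampled in the SAS MCMC procedure.

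The slit lamp section adopts the same model: "Biomicroscopy will be analyzed using the same Bayesian beta-binomial model as described for lens fit acceptance". The formula therefore bears on two of the four primary hypotheses, all of which must be met (section 2.3).

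Two notational points sit beside it. The index i runs over 1, 2, although y is already the two-eye total. The Model says p "is the probability of success (i.e., acceptable lens fitting"), while in the hypotheses p_T and p_C "are the probability of event (i.e., unacceptable lens fitting").

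**The concern.** A subject with an event in exactly one eye (y = 1) cannot come from MBern, which produces only 0 or 2. The mixture formula respects this and the augmented density does not. The excess weight depends on p and ρ, so it does not cancel from the posterior.

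A programmer who codes the augmented density as printed would let one-eye events be credited to the perfect-correlation component. Discordant eyes would then count as evidence for high ρ when they are evidence against it. The effective sample size falls, the credible interval for p_T − p_C widens, and a lens that meets the margin is more likely to miss it. One-eye events are realistic: the one Grade 3 slit lamp finding that section 14.2 reports from the interim data was in a single eye.

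**Working it through.** **Inputs (sections 2.3, 14.2, 14.5 and Table 11).** Per-eye event rate 5% for lens fit ("simulated with an unacceptable fitting rate of 5% (worse-case scenario") and 2% for slit lamp, the same in both arms; between-eye correlation 0.70; margins 0.10 and 0.05. Success means the upper bound of the central 95% credible interval is below the margin. Table 11 gives N = 140 and N = 240, each with 83% power. The target is 143 completers per arm. Assumption: the Table 11 sample sizes are totals split 1:1, as 286 = 2 × 143 is.

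**1. The density at y = 1.**
- z = 0: 2(1−ρ)p(1−p), which is correct.
- z = 1: ρ · √p · √(1−p) · C(2,1) = 2ρ√(p(1−p)). The mixture requires 0.
- At y = 0 and y = 2 the printed terms are correct, because C(2,0) = C(2,2) = 1.

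The total mass is therefore 1 + 2ρ√(p(1−p)). With ρ = 0.7:

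| p | Excess mass | Total mass | Weight at y = 1, mixture | Weight at y = 1, printed |
|---|---|---|---|---|
| 2% | 1.4 × √0.0196 = 0.196 | 1.196 | 0.6 × 0.0196 = 0.0118 | 0.208 |
| 5% | 1.4 × √0.0475 = 0.305 | 1.305 | 0.6 × 0.0475 = 0.0285 | 0.334 |

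The share of the printed y = 1 weight that goes to the component unable to produce it is 0.196/0.208 = 94% at 2% and 0.305/0.334 = 91% at 5%.

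**2. Reproducing Table 11.** A normal approximation with design effect 1 + ρ = 1.7 on 2n eyes per arm gives SE = √(p(1−p) × 1.7/n).
- Lens fit, n = 70: SE = √(0.0475 × 1.7/70) = 0.0340; 0.10/0.0340 − 1.96 = 0.98; power 83.8%.
- Slit lamp, n = 120: SE = √(0.0196 × 1.7/120) = 0.0167; 0.05/0.0167 − 1.96 = 1.04; power 85.1%.

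The full posterior was then computed by grid integration over the coefficients and ρ with the stated priors, 20,000 simulated trials per setting, all-zero trials counted as successes. The mixture gives 83.4% (lens fit) and 83.3% (slit lamp). Both match the stated 83%.

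**3. The printed density coded literally, same method.** N(0, 1000) is read as variance 1000, with SD 1000 in brackets.

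| Endpoint | Per arm | Mixture | As printed |
|---|---|---|---|
| Lens fit, 5% | 70 | 83.4% (82.9%) | 78.3% (77.6%) |
| Slit lamp, 2% | 120 | 83.3% (82.7%) | 78.4% (77.0%) |
| Lens fit, 5% | 143 | 98.2% (98.2%) | 97.2% (97.1%) |
| Slit lamp, 2% | 143 | 88.9% (88.0%) | 84.1% (83.3%) |

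A smaller run found that the slit lamp decision at 143 per arm differs between the two forms in about 6% of trials.

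**4. Two worked data sets, slit lamp, 143 per arm.**
- Test has 2 one-eye and 3 two-eye subjects; Control has 1 and 1. The upper bound is 0.047 under the mixture (pass) and 0.051 as printed (fail).
- Test has 2 one-eye subjects, Control has 1, and no subject has both eyes affected. The posterior mean of ρ is about 0.18 under the mixture and 0.89 as printed.

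**5. Lower rates and direction, 143 per arm.** At a 1% slit lamp rate, power is about 97.9% against 96.4%. For lens fit at 1% it is about 100% either way. With the true difference set at the margin, the printed form declares non-inferiority less often: 2.6% against 3.9% for slit lamp and 1.9% against 2.7% for lens fit.

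**The case against.** The strongest reply is that the restriction is already in the text. MBern is defined on 0 and 2 only, and Z = 1 means that the observation belongs to MBern, so y = 1 with Z = 1 is excluded by definition. On the permitted support the printed expression is exact, so the position of the binomial coefficient is not a second error. This stands: it is an omitted indicator, not a wrong model. It does not dispose of the point, because the printed density is the form developed for the MCMC step and, taken as it stands, it is not a probability distribution.

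Three stronger readings are tempting, and the documents do not support them.
- *The trial lacks its stated power.* The Table 11 figures match the mixture and not the printed density, which suggests that the sizing used the correct form. CLUE vision drives the target of 286, and at that size both safety endpoints stay above 80% even with literal coding.
- *The error could let an inferior lens through.* On average it works the other way, widening intervals and lowering the rate of false non-inferiority.
- *The mismatch in p changes the result.* The likelihood is unchanged under p → 1−p and y → 2−y, and the hypotheses define p_T and p_C separately as event probabilities. Harm would follow only if the p of The Model were carried unchanged into the decision rule, which would reverse its direction. The index is notation only.

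The 5% and 2% rates are also the plan's own worst cases. The prior studies showed no unacceptable fit and a single Grade 3 finding, so the likely effect is smaller than the table in the working.

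**Conclusion.** The concern holds as an error in a printed formula with a bounded consequence. The augmented density contradicts the mixture defined just before it and has total mass 1.196 to 1.305 at the planning values. The sizing stands.

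If the formula were coded literally, power at the Table 11 sample sizes would drop by about 5 points to about 78%. At 143 per arm, slit lamp power would drop from about 88–89% to 83–84% and lens fit power from about 98% to 97%, with about 6% of slit lamp decisions changing. The loss is about 1.5 points for slit lamp at a 1% rate and nil when no subject has a one-eye event.

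These figures assume ρ = 0.7, equal true rates in the two arms and the stated priors. Whether the stand-alone SAP repeats the formula cannot be told, since it is not among the documents. The correction is worth making because two primary safety conclusions rest on this likelihood.

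**What to change.** In protocol section 14.5, and in the stand-alone SAP if it repeats the formula, attach the indicator y ∈ {0, 2} to the z = 1 term; equivalently, set z = 0 whenever y = 1. A simpler route is to drop Z and code the three cells of the mixture directly:
- P(Y=0) = (1−ρ)(1−p)² + ρ(1−p)
- P(Y=1) = 2(1−ρ)p(1−p)
- P(Y=2) = (1−ρ)p² + ρp

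In the same edit, run the index over subjects, and define Y and p throughout as the unacceptable-fit event, so that p has the direction used in the decision rule.

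The cost is one formula and two definitions. Section 14.1 has the SAP finalised before database lock, so the correction can be made there without touching the design, the sample size or the data collected.

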### Bayesian Estimation and Statistical Evaluation of Hypothesis:

Non-inferiority of the Test lens relative to the Control lens with respect to lens fit acceptance will be evaluated using Bayesian statistics. The null and alternative hypotheses for evaluating non-inferiority of the Test lens relative to the Control lens with respect to lens fit acceptance are as follows:

$$\begin{aligned} H_0: p_T - p_C \geq 0.1 \\ H_A: p_T - p_C < 0.1, \end{aligned}$$

where  $p_T$  and  $p_C$  are the probability of event (i.e., unacceptable lens fitting) for Test lens and Control lens, respectively. Based on Bayesian posterior probability distribution of the proportion difference  $(p_T - p_C)$ , non-inferiority is interpreted as 95% probability of Test being no worse than Control by 10% (i.e.,  $p_T - p_C < 0.1$ ) with respect to unacceptable lens fitting rate. If the upper bound of the 95% central posterior credible interval is below 0.1, it can be concluded that there is 95% probability that the Test lens is non-inferior to the Control lens based on the observed sample.

In the case of all eyes have an acceptable lens fit (i.e., zero unacceptable lens fit), a Bayesian hierarchical model accounting for zero event problem will be considered. Details of this model will be provided in the stand-alone SAP.

### Biomicroscopy (Slit Lamp Findings)

Biomicroscopy will be analyzed using the same Bayesian beta-binomial model as described for lens fit acceptance. The proportion of eyes with clinically significant slit lamp findings (i.e., Grade 3 or higher, or significant corneal infiltrates) across study visits will be modeled.

# Clinical Study Protocol

## Johnson & Johnson Vision Care, Inc.

Bayesian Estimation and Statistical Evaluation of Hypothesis:

Non-inferiority of the Test lens relative to the Control lens with respect to slit lamp findings will be evaluated using Bayesian statistics. The null and alternative hypotheses for evaluating non-inferiority of the Test lens relative to the Control lens are as follows:

$$H_0: p_T - p_C \geq 0.05$$
$$H_A: p_T - p_C < 0.05,$$

where  $p_T$  and  $p_C$  are the probability of clinically significant slit lamp findings across study visits for Test and Control, respectively. Based on Bayesian posterior probability distribution of the proportion difference ( $p_T - p_C$ ), non-inferiority is interpreted as 95% probability of Test being no worse than Control by 5% (i.e.,  $p_T - p_C < 0.05$ ). If the upper bound of the 95% central posterior credible interval is below 0.05, it can be concluded that there is 95% probability that the Test lens is non-inferior to the Control lens based on the observed sample.

In the case of zero clinically significant SLF, a Bayesian hierarchical model accounting for zero event problem will be considered.

### 14.6. Secondary Analyses

#### Secondary Efficacy Analyses:

Secondary efficacy analyses will be conducted on the Per-Protocol (PP) population.

##### CLUE Overall Comfort and Overall Handling

CLUE overall comfort and handling will be analyzed using the same statistical method described for CLUE overall quality of vision.

##### Situational Visual Performance – Indoors

Situation visual performance – indoors will be assessed using the individual item “Clarity of vision indoors in bright light” ( [ ] ). Item responses will be converted into a binary variable for the purpose of analysis (Excellent = 1 and others = 0) and “Not applicable” response will not be considered in the analysis. The dichotomized item responses will be analyzed using a generalized linear mixed model with a binomial distribution and the logit as the link function. The model will include lens type as a fixed effect and site as a (G-side) random effect. Other subject characteristics such as age, gender, iris category, habitual lens type will be included when appropriate.

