**Clinical Study Protocol**  
**Johnson & Johnson Vision Care, Inc.**

Visit 1: Screening			
Step	Procedure	Details	
1.5	Habitual Wear Time	Record the average wearing time and comfortable wearing time.	
1.6	SCL Rx Confirmation	
The investigator confirms:
 
 
1. The subject is wearing a SCL Rx that has been confirmed current (up-to-date) within the prior 6 months.
 
2. The subject has worn the up-to-date SCL Rx for at least 2 weeks.
 
	
1.7	Eligibility after Screening	
All responses to Screening Inclusion Criteria questions must be answered “yes” and all responses to Exclusion Criteria must be answered “no” for the subject to be considered eligible.
 
If subject is deemed to be ineligible after screening, proceed to Final Evaluation and complete Subject Disposition. Refraction and Biomicroscopy forms do not need to be completed as part of Final Evaluation.
	

Visit 1: Baseline			
Step	Procedure	Details	
1.8	Baseline Questionnaire	
The subject will respond to the following Baseline Questionnaires based on their habitual lenses:
 
 
1. CLUE Baseline
 
	
1.9	Entrance Visual Acuity	Record the distance Snellen visual acuity (OD, OS, and OU) to the nearest letter with their habitual contact lens correction in place. Subjects must read the smallest line until at least 50% of the letters are read incorrectly.	
1.10	Remove Habitual Lens	The subject’s habitual lenses will be removed and stored in their own lens case. If they forgot to bring their lens case, one will be provided to them.	

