##### CLUE Overall Quality of Vision

CLUE vision scores will be analyzed using a linear mixed model to compare the Test and Control lenses at the 2-week follow-up evaluation. The model will include baseline CLUE vision score and lens type as fixed effects and clinical site as a random effect (G-side). Other subject characteristics such as age, gender, iris category (dark iris and light iris), and habitual lens type (habitual daily disposable and habitual daily wear reusable) will be included when appropriate. The Kenward and Roger method will be used for the denominator degree of freedom.

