# Clinical Study Protocol

## Johnson & Johnson Vision Care, Inc.

2-sided 95% confidence interval is above 0.67. If non-inferiority of the Test lens over Control lens is met, then superiority will be assessed. If the lower bound is above 1.0, then superiority of the Test lens over the Control lens can be concluded.

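### The indoor-clarity model prespecifies no baseline vision score, although one is collected before randomisation; adding it would gain some precision, provided the 0.67 margin is then tested on a standardised (marginal) odds ratio

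*Combined protocol and SAP*

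**What the plan says.** Section 14.6 (Situational Visual Performance – Indoors) codes the item as Excellent against every other rating, drops Not Applicable answers, and fits a logistic mixed model: "The model will include lens type as a fixed effect and site as a (G-side) random effect". It adds: "Other subject characteristics such as age, gender, iris category, habitual lens type will be included when appropriate". No baseline score appears.

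Section 14.5 treats CLUE vision differently: "The model will include baseline CLUE vision score and lens type as fixed effects". Section 14.6 applies the same method to CLUE comfort and handling.

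The baseline questionnaire is given at step 1.8 of Visit 1 (section 7.2): "The subject will respond to the following Baseline Questionnaires based on their habitual lenses". The only one listed is "CLUE Baseline". The lens is assigned later, at step 1.16, and section 5.1 requires baseline information to be in hand before randomisation.

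Non-inferiority is judged by the lower 95% limit of the odds ratio against 0.67. A superiority step follows: "If the lower bound is above 1.0, then superiority of the Test lens over the Control lens can be concluded". Table 12 gives 93% power for non-inferiority and none for superiority.

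**The concern.** Indoor clarity is self-rated vision, so a self-rated vision score taken before randomisation is a natural prognostic covariate. Of the four questionnaire endpoints that compare the two lenses, this is the only one without a baseline term, and the documents give no reason. The optional list is open-ended. It allows a baseline score but does not prespecify one, so adding it after the data are seen would be a post hoc choice.

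Precision is at stake, chiefly for the superiority step, which has low power at the planning rates. Validity is not at stake: randomisation protects the unadjusted comparison.

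**Working it through.** **Inputs.** Excellent rates of 60% (Test) and 50% (Control), and odds-ratio margin 0.67 (section 14.2); 143 completers per arm (Table 12 and the text below it); lower limit of a two-sided 95% interval (section 14.6). The correlation between baseline score and rating is an assumption, taken over 0 to 0.6 on the latent scale behind the rating.

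**1. Reproduce the stated power.** Odds ratio = (0.60/0.40)/(0.50/0.50) = 1.50, log = 0.405; log 0.67 = −0.400.
SE = √[1/(143×0.60×0.40) + 1/(143×0.50×0.50)] = √(0.0291 + 0.0280) = 0.239.
Non-inferiority power = Φ[(0.405 + 0.400)/0.239 − 1.96] = Φ(1.41) = 92.1%. Risk-difference forms of the same margin give 92.3–92.7%. Table 12 says 93%, so the figure is reproduced.

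**2. Superiority on the same inputs, no baseline term.** Φ(0.405/0.239 − 1.96) = Φ(−0.26) = 39.6%.

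**3. Superiority with the baseline score.** Latent-threshold simulation, 3,000 trials per setting, logistic regression, marginal rates held at 60% and 50%, site omitted. Without the covariate, power was about 38–40%.

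| Latent correlation (assumed) | Superiority power, adjusted |
|---|---|
| 0 | no gain |
| 0.3 | 41% |
| 0.4 | 42% |
| 0.5 | 46% |
| 0.6 | 50% |

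Monte Carlo error near 40% is √(0.4×0.6/3000) = 0.9 points, so the gain at 0.3 is barely visible.

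**4. The conditional odds ratio against 0.67.** In a logistic model a prognostic covariate increases the standard error of the log odds ratio. Power rises only because the conditional odds ratio also lies further from 1 than the marginal one. If the lenses are equal, both odds ratios are 1 and only the larger standard error remains. Non-inferiority power with the baseline term, tested conditionally:

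| True rates | No baseline term | r = 0.4 | r = 0.5 | r = 0.6 |
|---|---|---|---|---|
| 50% v 50% | about 38–40% | 36% | 33% | 32% |
| 55% v 50% | 71% | 70% | – | 67% |
| 60% v 50% | about 92% | about 92% | about 92% | about 92% |

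At a true marginal odds ratio of 0.67, one-sided type I error falls from 2.1–2.7% to about 1.7–1.9% (r = 0.4) and 0.8% (r = 0.6). The test has become stricter than the one planned.

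**5. The meaning of the margin.** With Control at 50%, odds of 0.67 correspond to a rate of 0.67/1.67 = 40.1%, which is 9.9 points lower. This is the 10% difference by which section 14.2 justifies 0.67, and it is a marginal statement.

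**6. Baseline-adjusted marginal odds ratio.** Fit the model with baseline, average the predicted probabilities under each lens over all subjects' baseline values, and form the odds ratio from the two averages. In simulation, one-sided type I error at 0.67 was 2.2–2.8%. Non-inferiority power was 93–97% at 60% v 50% and 41–49% at 50% v 50%. The superiority gain was the same as in step 3.

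**The case against.** Several objections carry weight.

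- A reader might infer that adding the covariate costs nothing, because non-inferiority power stays at 92–93%. That holds only if Test is truly better. The hypothesis listed for this item in section 2.3 is non-inferiority, and step 4 shows a loss when the lenses are equal. The lower type I error in the conditional test comes from the same effect and is no reassurance. This objection stands against simple adjustment; standardising answers it.
- The margin was justified marginally, with an uncovaried chi-square calculation. The planned model is already conditional on site and any optional covariates, but nothing in the documents suggests that these are strongly prognostic, so that reply is weak. The standardised odds ratio keeps the margin's meaning.
- The correlation may be modest. Baseline is a multi-item score on the habitual lenses, whereas the outcome is one dichotomised item on different lenses. At 0.3–0.4 the gain is only about 1–2 points. This stands.
- Superiority on this item is not among the hypotheses in section 2.3 and is not powered in Table 12. The 40% also reflects cautious planning rates: at the historical adjusted rates in Table 10 (63% v 47%) power is about 78% without the covariate and 79–88% with it. So 40% does not show that the trial is underpowered for its stated hypothesis.
- Section 14.1 defers detail to a stand-alone SAP, so the omission may not be final.

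**Conclusion.** The point holds as a modest efficiency gain on a secondary endpoint. Baseline CLUE vision is available before randomisation and is used for CLUE vision, yet it is not prespecified for indoor clarity. At the planning rates the forgone superiority power runs from nothing at zero correlation to about 10 points (40% to 50%) at a latent correlation of 0.6. That correlation is assumed, and the simulations omit site.

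The documents do not support two stronger readings. One is that the planned analysis is biased or invalid: it is a legitimate comparison that leaves information unused. The other is that the covariate can simply be added and the model odds ratio read against 0.67, which lowers non-inferiority power if the lenses are alike. The recommendation is sound only with the standardised odds ratio as the test itself, not as an optional extra.

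**What to change.** In section 14.6 and the stand-alone SAP:

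- Prespecify baseline CLUE vision score as a fixed covariate in the indoor-clarity model.
- Base both the 0.67 non-inferiority test and the superiority test on the marginal odds ratio obtained by standardising the fitted model over the observed baseline distribution, with a delta-method or influence-function 95% confidence interval. State how site and any other covariates enter the standardisation.
- State that 0.67 refers to this marginal odds ratio, in line with section 14.2.

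No new data are needed. The cost is a short SAP addition and slightly more programming, because the interval no longer comes straight from the model output. Section 14.1 has the SAP finalised before database lock, which leaves room for the change.
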